The generation of knowledge regarding the usefulness of metformin in this specific group of patients can lay the groundwork for research on the effect of this drug in solid tumors and other pediatric neoplasms.

HYPOTHESIS

If metformin is added to standard chemotherapy during the remission induction phase in Mexican adolescents with newly diagnosed ALL, then it will decrease the level of ABCB1/MDR1 gene mRNA expression and increase AMPK expression levels, at the end of this treatment period.

OBJECTIVES

General:

- To evaluate the efficacy of metformin in modifying ABCB1 and AMPK gene expression in adolescents diagnosed with ALL during the remission induction phase.

Specific

- To describe the expression levels of ABCB1/MDR1 and AMPK genes in adolescents with ALL at diagnosis and in healthy controls.
- To compare the expression levels of ABCB1/MDR1 and AMPK genes at diagnosis and at the end of induction in adolescents with ALL treated with conventional chemotherapy and those additionally treated with metformin.
- To compare overall and disease-free survival in adolescents with ALL treated in relation to ABCB1/MDR1, and AMPK gene expression.
- To compare overall and disease-free survival in adolescents with ALL treated with conventional chemotherapy with those treated with conventional chemotherapy plus metformin.

METHODOLOGY

Type and design of study

Type of study: randomized clinical trial

Study design: analytical, experimental, longitudinal and prospective study.

Population

The population to be studied are patients with newly diagnosed ALL between 10 and 21 years.

Eligible population: patients with newly diagnosed ALL between 10 and 21 years old, diagnosed at the Hospital General de México "[name]" from February 2021 to December 2023.

Inclusion, exclusion and elimination criteria

- Inclusion criteria:
 1. Patients aged between 10 and 21 years with a new diagnosis of ALL at the Hospital General de México, [name].
 2. Patients and legally authorized person who sign the informed consent.

- Exclusion criteria:
 1. Patients with antineoplastic treatment prior to admission.
 2. Patients with Down syndrome.

- Elimination criteria:
 1. Patients who abandon treatment for more than a few weeks.4
 2. Patients who withdraw informed consent

Sample size

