To calculate the sample size, we used data from the publication by Ramos Peñafiel⁶³, where a decrease in the expression pattern of ABCB1 gene expression from high to low expression after metformin administration was 50%.

The sample size calculation was based on the formula for estimating a proportion, with a confidence level of 95% and a precision of 5%:

$$n = \frac{Z_{\alpha}^2 * p * q}{d^2}$$

A sample number of 8 patients in each group is obtained, assuming a loss of 20%, 10 patients are calculated for each group.

Definition of the variables to be evaluated and how they are to be measured

Variable	Conceptual Definition	Unit of measurement	Type of variable	Coding
Age	Time elapsed in years since birth.	Years	Quantitative	Not applicable

Gender	Male or female phenotype of the person.	Male/female	Qualitative Dichotomous	0: male 1: female
Leukocyte count at diagnosis	Number of total leukocytes reported on complete blood count at diagnosis.	X10/ml ³	Quantitative	Not applicable
Hemoglobin at diagnosis	Measurement of the amount of oxygen transport protein reported in initial complete blood count.	g/dL	Quantitative	Not applicable
Platelet count at diagnosis	Measurement of the number of platelet fragments produced by the megakaryocytes, reported in the initial complete blood count.	X10/ml ³	Quantitative	Not applicable
Immunophenotype of leukemia lymphoblastic	Cellular variant of acute lymphoblastic leukemia	B/ T	Qualitative dichotomous	0: strain B 1: lineage T
Cytogenetic alterations	Alterations in the genetic structure of leukemic cells.	None/ t(9;22)/ t(12,21)/ t(4,11), other	Qualitative polytomous	0: none 1: t(9;22), 2: t(12,21) , 3: t(4,11), 4: other
MDR-1 and AMPK gene expression.	Amplification of gene expression by RT-PCR	No expression / low expression / high expression expression	Qualitative polytomous	0: not expressed 1: high expression 2 low expression
Pre-phase response with prednisone	Decrease in total peripheral blood blast count less than 1000 after 7 days of steroid (day 0)	Present/absent	Qualitative dichotomous	0: Yes 1: No
Morphological status at day +14	Presence of blasts in bone marrow sample per day +14 referral induction	M1, M2, M3	Qualitative polytomous	0: M1 1: M2 2: M3
Morphological response at the end of induction	Presence of blasts in the bone marrow aspirate at the completion of remission induction phase.	M1, M2, M3	Qualitative polytomous	0: M1 1: M2 2: M3

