Minimal residual disease at the end of induction.	Flow cytometry measurement of the presence of 1x10 ⁻³ blasts.	Positive /Negative	Qualitative dichotomous	0: positive 1: negative
Relapse	Presence of blasts in bone marrow after remission has been achieved.	Present/absent	Qualitative dichotomous	0: absent 1: present

Time to relapse	Time from diagnosis of leukemia to relapse	Days	Quantitative	Not applicable
Death	Cessation of life	Present/absent	Qualitative dichotomous	0: absent 1: present
Time to death	Time from leukemia diagnosis to death	Days	Quantitative	Not applicable

Table 1. Variable definitions.

PROCEDURES

Patients with a newly morphological diagnosis of ALL at the Hospital General de México "[name]" will be invited to participate in this trial, and informed consent will be requested from parents and participants.

The data collection is obtained from the patients chart such as age, gender, leukocyte count, hemoglobin, platelet count and immunophenotype.

Peripheral blood samples will be collected in EDTA tube. The sample will be centrifuged obtaining mononuclear cells, and the analysis of ABCB1 and AMPK expression will be performed. This will be done on samples obtained before the start of treatment and at the end of the induction phase. Samples will be collected by peripheral vein puncture, and mononuclear cells will be separated using density gradient. Mononuclear cells are separated and suspended in PBS medium and stored at -70°C . RNA isolation is performed using TRIzol® (Invitrogen/life Technologies), and will be stored at -80°C until use. For cDNA synthesis, 2g of RNA, final volume of 20L will be combined with 200U of MMLV RT enzyme (Invitrogen, Carlsbad, CA, USA).

Expression of mRNA levels will be measured using the TaqMan gene expression assay (Applied Biosystems Foster city, CA, USA). The cut-off point between low and high expression will be determined according to mean values obtained in healthy controls, selected during case recruitment in a 2:1 ratio for each case.

Regarding treatment, patients will be randomized into 2 groups, where in both cases the conventional remission induction treatment will be given, and to intervention group metformin will be added at a dose of 1000mgm2Seday, divided into two doses, with a maximum dose of 850mg every 8 hour, orally.

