The Kolmogorov-Smirnov test will be performed for continuous variables to determine if they have normal distribution; if they have normal distribution, both groups will be analyzed by means of the t-student test; if they do not have normal distribution, the chi-square test, Fisher's exact test and Mann Whitney U test will be used for the bivariate analysis. To compare the expression of ABCB1/MDR1 and AMPK genes at the time of diagnosis and at the end of induction, McNemar's test will be used.

For the calculation of the overall and disease-free survival function, the Kaplan Meier survival test will be used for both groups and the differences between groups will be analyzed by means of the log Rank test, both for overall and disease-free survival. Similarly, the overall and disease-free survival function will be analyzed with the Kaplan Meier test and log rank for ABCB1/MDR1 and AMPK gene expression.

ETHICAL AND BIOSAFETY ASPECTS

According to the General Health Law regarding research on human subjects, this protocol is considered a higher than minimal risk research, since randomized methods of assignment to therapeutic schemes are used.

This protocol takes into account the Mexican General Health Law regarding the provision of health care services and health research, as well as national and international ethical standards.

This study will be carried out with strict observance of recognized scientific principles and respect and confidential handling of the data obtained. The security mechanisms to maintain the ethical aspects of this study are:

1. Review of this protocol by the research and ethics committees of the Hospital General de México "[name]".
2. All information obtained in this study will be made available to the Ethics and Research Committees.
3. The confidentiality of the study information is assured, as well as the identity of the patients. The identification data of the participants will be codified, assigning a consecutive participation number. The identification information and the relation between the identification numbers and the data obtained will be known only to the participating investigators and will be preserved confidentially in electronic media.
4. There will be no charge for the study, nor will there be any consistency for participation in this study. Refusal to participate in the study will not influence the patient's treatment or clinical care.

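### The elimination rule and the paired test leave the expression result to patients with both samples who stay on treatment; the 20% allowance restores numbers, not the randomised comparison

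*Combined protocol and SAP*

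**What the plan says.** No endpoint is labelled primary, but the general objective is clear: "To evaluate the efficacy of metformin in modifying ABCB1 and AMPK gene expression in adolescents diagnosed with ALL during the remission induction phase". The hypothesis places the expected change at the end of induction.

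- **Measurement (PROCEDURES).** Expression is assayed twice: "This will be done on samples obtained before the start of treatment and at the end of the induction phase". The schedule at the end of the document shows the same two time points and none between them.
- **Coding (variable table).** Expression is coded as none, high or low. There is no code for death or for a missing sample.
- **Test (STATISTICAL ANALYSIS).** For the comparison of expression "at the time of diagnosis and at the end of induction, McNemar's test will be used". Fisher's exact test is listed among the tests for bivariate comparisons.
- **Elimination criteria.** There are two: withdrawal of consent, and "Patients who abandon treatment for more than a few weeks" (the number of weeks is displaced in the extracted text). Neither refers to when the expression outcome is measured. Death is not listed.
- **Loss (Sample size).** "A sample number of 8 patients in each group is obtained", and then "assuming a loss of 20%, 10 patients are calculated for each group".

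The statistical section names no analysis population, no approach to missing second samples and no sensitivity analysis. Deaths and relapses are followed for 12 months and enter only the survival analyses.

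**The concern.** Patients leave the expression analysis by two routes.

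The first is the elimination rule. Read literally, a patient who gave both samples and then abandoned treatment in consolidation is removed, although the outcome is fully observed. Nothing is gained by that, and it lets events after the outcome decide who is counted.

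The second is a missing second sample. McNemar's test uses complete pairs, so death, abandonment or withdrawal during induction, or a failed sample, all end in exclusion without a stated rule.

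Randomisation protects the comparison of everyone assigned. It does not protect a comparison of those who completed induction, gave a second sample and stayed on treatment. Adding two patients per group restores the intended number of pairs, but it cannot show whether the lost patients resembled those who stayed. With groups this small, a few unobserved patients can move a result across the usual threshold. If the handling is not fixed in advance, it can be chosen after the data are seen.

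**Working it through.** **Inputs.** From the Sample size section: 8 evaluable per group, 20% loss, 10 per group, and an expected 50% moving from high to low ABCB1. Assumed here: the 20% falls equally on both arms and entirely before the second sample. The observed counts are illustrative, and every patient in them is taken to have high ABCB1 at baseline, so that each could shift.

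**The plan's own figures.** The loss step reproduces: 8 / (1 − 0.20) = 10 per group, so 2 of 10 per arm, or 4 of 20 in all, may be unscored. The base of 8 does not follow from the stated formula at 5% precision: 1.96² × 0.5 × 0.5 / 0.05² = 384.1. That is a separate matter, and 8 is taken as given here.

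**Between arms, one example (two-sided Fisher exact test).**

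| Handling of 2 lost per arm | Metformin | Control | Difference | p |
|---|---|---|---|---|
| Completers only | 6/8 | 1/8 | 62.5 points | 0.041 |
| All lost scored as no favourable shift | 6/10 | 1/10 | 50 points | 0.057 |
| Worst case for metformin | 6/10 | 3/10 | 30 points | 0.37 |
| Best case for metformin | 8/10 | 1/10 | 70 points | 0.005 |

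**Between arms, all completer results.** With 8 v 8 completers and metformin ahead, 10 possible results reach p ≤ 0.05.
- Worst case: 9 of the 10 lose significance. Only 8/8 v 0/8 survives (p = 0.023).
- All lost scored as no favourable shift: 3 of the 10 lose it. These are 6/8 v 1/8 (0.041 to 0.057), 7/8 v 2/8 (0.041 to 0.070) and 8/8 v 3/8 (0.026 to 0.070). The other 7 stay significant.
- Best case: 7 non-significant results become significant, for example 4/8 v 0/8 (0.077 to 0.011).

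**Within one arm.** If 4 of 8 completers shift, the proportion among the 10 randomised lies between 4/10 and 6/10. For McNemar (exact), 6 v 0 discordant pairs gives p = 0.031. Lost patients scored as unchanged are concordant and leave that p-value as it is. Only if both had changed in the opposite direction (6 v 2) does it rise to 0.29.

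**Size of a possible bias.** With a true shift of 50% and loss rates *a* in patients who shift and *b* in those who do not, the observed shift is 0.5(1 − a) / [0.5(1 − a) + 0.5(1 − b)]. Two assumed patterns, each giving 20% loss overall:
- a = 0.10, b = 0.30: 0.45 / 0.80 = 56%.
- a = 0, b = 0.40: 0.50 / 0.80 = 63%.

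**The case against.** Several points on the other side are sound.

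- **The 20% is not broken down.** Follow-up runs for 12 months and the second sample falls near day 29 of the schedule, so some loss may come after both samples. Two missing pairs per arm is therefore an assumption. It is also only inferred that a patient eliminated late would leave the expression analysis, because the criteria do not say which analysis elimination applies to.
- **The bounds are extremes.** Under the milder scoring, 7 of the 10 significant results survive. A bias from 50% to 56% is small beside sampling error: the exact 95% interval for 4/8 is 16% to 84%. Much of the fragility comes from the group size.
- **Scoring every lost patient as a failure is not a safe main analysis.** It leaves McNemar unchanged, as shown. If loss is heavier in controls it can create a positive result: 8/10 v 2/8 (p = 0.054) becomes 8/10 v 2/10 (p = 0.023). It also counts patients without high baseline ABCB1, who cannot move from high to low.

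A reader might infer that loss is known to depend on expression or on arm, because the background links ABC transporters to resistance and names gastrointestinal and metabolic side effects of metformin. The documents do not support that. The same background calls the pediatric evidence controversial and describes metformin as safe with acceptable toxicity. Informative loss is plausible, not shown.

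These points limit the size of the problem and the choice of remedy. They do not supply the missing rule.

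**Conclusion.** The concern holds in a limited form, and the plan should be changed. The elimination rule ignores whether the outcome has already been measured, the paired test omits anyone without a second sample, and the only provision for loss is a larger group. At 2 of 10 unscored per arm, an apparent difference of 62.5 points could be anything from 30 to 70 points among those randomised. That range rests on equal loss in the arms, all of it before the second sample, and on illustrative counts.

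Two stronger readings should be resisted. A reader might infer that the plan orders deaths to be dropped. It does not: death is not an elimination criterion, and such patients leave only because no second value exists. A reader might also infer that the within-arm McNemar result is bound to collapse. It changes only if the unseen patients moved in the opposite direction, and nothing in the documents says they would.

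**What to change.** 1. **Elimination criteria.** Add a clause that every randomised patient with both samples stays in the expression analysis, in the assigned arm, whatever happens later, unless consent to use the data is withdrawn.
2. **STATISTICAL ANALYSIS.** Keep the complete-pair analysis. Add a pre-specified sensitivity analysis giving best-case and worst-case bounds by arm for patients without a second sample. Scoring them as no favourable shift can be one scenario, but not the lead analysis. Take the high-to-low ABCB1 proportion among patients with high expression at baseline.
3. **Reporting.** Give by arm the number without a second sample and the reason: death, abandonment, withdrawal or failed sample.

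The cost is one clause, a few sentences and a little more analysis. It needs no extra patients, visits or assays. The headline result may look less certain than the complete-pair figure alone.

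### Gene expression is measured as a level but defined only as none/high/low, and the one test assigned to it (McNemar) does not compare the randomised arms

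*Combined protocol and SAP*

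**What the plan says.** The Hypothesis section predicts that adding metformin means that "it will decrease the level of ABCB1/MDR1 gene mRNA expression and increase AMPK expression levels". The second specific objective compares expression levels, at diagnosis and at the end of induction, in patients "treated with conventional chemotherapy and those additionally treated with metformin". The question is therefore about levels, and about a difference between randomised arms.

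Procedures: "Expression of mRNA levels will be measured using the TaqMan gene expression assay". It also says: "The cut-off point between low and high expression will be determined according to mean values obtained in healthy controls". Numeric values must therefore exist before any patient can be called low or high.

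Table 1 types the expression variable as qualitative with three levels: "0: not expressed 1: high expression 2 low expression". It contains no quantitative expression variable.

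Statistical analysis makes three statements that bear on this:
- For continuous variables that pass a normality test, "both groups will be analyzed by means of the t-student test". If they do not, chi-square, Fisher's exact and Mann-Whitney are listed. Expression is not named.
- McNemar's test is named for expression at diagnosis against the end of induction.
- Kaplan-Meier curves and log-rank tests are planned by expression group. Expression is the grouping factor there, not the outcome.

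The Sample size section rests on a published change "from high to low expression after metformin administration was 50" per cent, and on a proportion formula "with a confidence level of 95% and a precision of 5" per cent. It states 8 per group, raised to 10 for 20% loss.

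**The concern.** A randomised trial should state how its main outcome will be compared between arms. Here the only test tied to that outcome looks within patients over time. Both arms receive intensive induction chemotherapy, and the Problem statement says that the variation of expression during treatment is unknown. A before-after change in the metformin arm therefore cannot be credited to metformin without setting it against the control arm.

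Two further gaps follow from Table 1. McNemar's test in its standard form needs two levels, while the table has three. The low/high boundary is defined, but there is no none/low boundary and no merging rule. Nor does the plan say how results on the two genes are judged together.

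At stake is whether the trial answers its own question. One possible route invites a false claim from a result in one arm only. Another compares the arms but discards most of the information in the measured value.

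**Working it through.** **The plan's own figure.** With p = q = 0.5, z = 1.96 and d = 0.05, n = 1.96² × 0.25 / 0.05² = 384.2, rounded up to 385. The stated 8 does not follow. With n = 8, d = 1.96 × √(0.25/8) = 0.346, a precision of about 35%. The loss step does reproduce: 8 / (1 − 0.20) = 10. I use 8 and 10 per arm below because those are the planned numbers.

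**Route 1: a separate McNemar test in each arm.** For one-way changes, the two-sided exact p-value with k changes is 2 × 0.5^k. Five changes give 0.0625 and six give 0.031, so at least six are needed. If a fraction q of all patients in an arm switches and none moves back, the chance of significance is s = P(Bin(n, q) ≥ 6). If both arms share the same q, metformin has no effect, and the chance that exactly one arm is significant is 2s(1 − s).

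| q in both arms (assumed) | n = 10: s | exactly one arm | n = 8: s | exactly one arm |
|---|---|---|---|---|
| 50% | 0.377 | 47% | 0.145 | 25% |
| 40% | 0.166 | 28% | 0.050 | 9% |
| 30% | 0.047 | 9% | 0.011 | 2% |
| 20% | 0.006 | 1% | 0.001 | 0.2% |

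Half of each figure is metformin-only significance: at q = 50%, 23.5% for n = 10 and 12.4% for n = 8. The s column also gives one-arm power: 38% and 14% at 50% switching.

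**Route 2: Fisher's exact test between arms on the categories.** With 50% of metformin patients switching and an assumed 0, 10 or 20% of controls, power is 62, 30 or 13% at 10 per arm and 36, 22 or 12% at 8.

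**Route 3: the measured value.** The documents give no SD, diagnosis/end correlation or baseline offset, so these are assumed: normal log values, correlation 0.2 to 0.8, baseline 0 to 1 SD above the control mean, and 40 healthy controls (2:1 for 20 patients). Fisher is applied to end-of-induction high/low. Simulated power:

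| Setting | t-test | Fisher on high/low |
|---|---|---|
| 10 per arm, 1 SD | 55-58% | 18-21% |
| 10 per arm, 1.33 SD | 79-81% | 31-41% |
| 10 per arm, 2 SD | 99% | 51-80% |
| 8 per arm, 1.33 SD | 69-71% | 22-40% |
| 10 per arm, 1.33 SD, heavy tails (t, 3 df) | 85% | 39-74% |

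From the noncentral t distribution, two-sided 5% and 80% power, the unadjusted comparison detects 1.32 SD at 10 per arm and 1.51 SD at 8.

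**Adjusting for the diagnosis value.** At 1.33 SD and 10 per arm, adjusted power is 78, 79, 81, 88 and 99% for correlations of 0, 0.2, 0.3, 0.5 and 0.8, against 80% unadjusted. Adjustment helps only above a correlation of about 0.3. At correlations of 0 to 0.2 it costs about 1 to 3 points at 10 per arm (80.3 against 79.3 and 77.6) and about 2 to 4 at 8 per arm (69.7 against 67.8 and 66.0).

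**The case against.** The strongest reply is that the plan already holds the needed tests. It speaks of analysing both groups, lists four two-group tests, and its objectives set the comparison between arms. This stands in part: a reader who infers that the plan contains no between-arm test at all goes too far. The list is not assigned to expression, though, and it places chi-square and Fisher under non-normality of continuous variables. Applied with Table 1's typing, it leads to chi-square or Fisher on categories, not to the level named in the hypothesis.

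A reader might also infer that the trial has a 47% chance of a false result. The documents do not support that. The figure requires separate within-arm tests, which the plan does not state, and equal switching of half of all patients in both arms, whereas the cited 50% was observed after metformin. It also counts trials in which only the control arm is significant. The table above shows how steeply it falls at lower rates.

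The 50% has no stated denominator. If it refers to patients who start high, and 70% do (assumed), then 35% of all patients switch: one-arm McNemar power falls to 9% (n = 10) or 3% (n = 8), and Fisher against 0% in controls to 25% or 11%.

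Finally, the comparison of Fisher with the measured value rests on assumed inputs throughout, and the sample-size event is a high-to-low change rather than end-of-induction status. That is fair: the direction of the loss is general, but its size is illustrative. The gap narrows with heavy tails or very large shifts.

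**Conclusion.** The point holds from the text alone: a level is hypothesised and measured, only categories are defined, and the one test assigned to the outcome does not compare the arms. Significance in one arm only would not be evidence of a metformin effect. How often that happens without any effect depends on the switching rate: from 47% down to 1% at 10 per arm, and from 25% down to 0.2% at 8, for rates of 50% down to 20%. If the categories are compared between arms instead, power is generally lower than on the measured value: about 31-41% against 80% at 1.33 SD and 10 per arm. Switching rates, SD, correlation and baseline offset are assumptions.

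The mismatch between 385 and 8 is a separate defect and adds no weight here. It matters only because changing the main analysis means restating the sample-size basis. The change should be made before the data are analysed, and it is a clarification rather than a redesign.

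**What to change.** 1. **Table 1.** Add the measured value of each gene as a quantitative variable, on the log scale and normalised as for the low/high cut-off. Write down that normalisation method and a pre-stated value for non-detected samples.
2. **Procedures.** Reconcile the sample source first. One paragraph describes peripheral blood at both times; a later one lists end-of-induction expression with the marrow aspirate. Both values must come from the same tissue before one is adjusted for the other.
3. **Statistical analysis.** For each gene, compare the end-of-induction value between the randomised arms, two-sided 5%, adjusted for the diagnosis value, with Mann-Whitney as sensitivity analysis. An unadjusted t-test is acceptable if the correlation is expected to be low.
4. **Two genes.** State before the data are seen whether both must succeed (each at 5%) or either suffices (2.5% each). This is the sponsor's choice. Requiring both lowers joint power: 0.80 × 0.80 = 64% if the genes are independent.
5. **High/low.** Keep it, with a stated two-level rule, as a secondary description and for the survival groups. State that McNemar is within-arm only and is not the arm comparison.
6. **Sample size.** Replace the basis with what the main analysis can detect: 1.32 SD at 10 per arm and 1.51 SD at 8, per gene, unadjusted, 80% power at 5%. If alpha is split, these become 1.48 and 1.70 SD.

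The cost is wording in three sections and the written normalisation method; no new patients, samples or assays are needed. The downside is that the main result is no longer the high-to-low proportion on which the sample size was based. Many non-detected samples would also shrink the gain: with 43-80% of end-of-induction metformin samples at the floor (correlation 0.5, 1.33 SD, 10 per arm), simulated power is 67-84% adjusted against 24-40% for Fisher.

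### With a healthy-mean cut-off and only a before/after test named, a high-to-low shift in expression can be significant without any metformin effect; the test should be between arms

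*Combined protocol and SAP*

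**What the plan says.** - **Cut-off (Procedures).** "The cut-off point between low and high expression will be determined according to mean values obtained in healthy controls". These controls are "selected during case recruitment in a 2:1 ratio for each case". The section does not say whether the mean is taken on relative quantities or on delta-Ct values, whether a margin is added, or when the cut-off is fixed.
- **Coding (Table 1).** Expression of each gene has three categories: "No expression / low expression / high expression expression".
- **Assay (Procedures).** Mononuclear cells are separated by density gradient, before treatment and at the end of induction. No step that selects blasts is described.
- **Expected effect (Sample size).** The calculation takes from a cited study that the "decrease in the expression pattern of ABCB1 gene expression from high to low expression after metformin administration was 50" per cent.
- **Objective (Objectives, Specific).** Expression at diagnosis and at the end of induction is to be compared between patients on conventional chemotherapy and those who also receive metformin.
- **Tests (Statistical analysis).** McNemar's test is named for diagnosis against end of induction. Whether it is run by arm or on all patients together is not stated. The t, chi-square, Fisher and Mann-Whitney tests are listed for two-group analysis in general, but none is tied to the change in expression. Survival "will be analyzed with the Kaplan Meier test and log rank for ABCB1/MDR1 and AMPK gene expression"; which sample supplies the label is not stated.

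**The concern.** The high/low label supports the description against controls, the before/after change and the survival groups. A cut-off at the control mean runs through the normal range. Induction is meant to clear blasts, so the late sample may consist largely of normal cells, and its label then depends mainly on where the cut-off falls among healthy people. A patient can pass from high to low because the cell mix changed.

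A before/after test in the metformin arm cannot separate that from a drug effect. At stake is the trial's main conclusion, that metformin lowers ABCB1/MDR1 expression. The same applies to AMPK, in whichever direction leukaemic and normal cells differ.

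**Working it through.** **1. The plan's own figure.** Inputs from the Sample size section: p = q = 0.5, 95% confidence (z = 1.96), d = 0.05.

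n = z²pq/d² = 3.8416 × 0.25 / 0.0025 = 384.2, so 385 per group, not the stated 8. The allowance for loss is right: 8 / 0.8 = 10. The mismatch is a separate error and nothing below depends on it. I use the stated 8 and 10 per arm.

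**2. Share of healthy people labelled 'high'.** The plan gives no spread or shape, so these are assumptions. For a symmetric distribution the share above the mean is 50%. For log-normal values with log SD s it is 1 − Φ(s/2):

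| log SD | share 'high' |
|---|---|
| 0.5 | 40% |
| 1.0 | 31% |
| 1.35 | 25% |
| 2.0 | 16% |

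The estimated cut-off also varies. With 40 controls (2 per case × 20 cases) and log SD 1, the true share above it covers about 19% to 46% in 95% of simulated control samples. If 2:1 means two cases per control, there are 10 controls and the range is about 11% to 62%.

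**3. Shift with no drug effect.**
- *Stable expression, cut-off at the centre.* Under bivariate normality with before/after correlation ρ, P(low later | high first) = 0.5 − arcsin(ρ)/π, which is 50% at ρ = 0 and 33% at ρ = 0.5. As a share of all patients, high-to-low is at most 0.5 × 0.5 = 25%, balanced by equal low-to-high movement. McNemar's null hypothesis already allows for this.
- *Return to healthy levels.* Suppose all patients start high and the late value behaves like a healthy person's. If 50% to 25% of healthy people are 'high', then 50% to 75% of patients become low, with nothing moving the other way.

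**4. McNemar's exact test within one arm, second scenario.** With k moves, all in one direction, two-sided p = 2 × 0.5^k: 0.0625 for k = 5 and 0.031 for k = 6. The test therefore rejects when at least 6 patients shift.

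| n in arm | 50% shift | 75% shift |
|---|---|---|
| 10 | 386/1024 = 38% | 92% |
| 8 | 37/256 = 14.5% | 68% |

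With 80% high at diagnosis, n = 10 and ρ = 0, the test rejects 9% (healthy share high 50%) to 46% (25%).

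Running McNemar's test in each arm and setting the results side by side does not solve this. With n = 10 and a 50% shift in both arms, the chance of significance in the metformin arm only is 0.377 × 0.623 = 23%.

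**5. Fisher's exact test between arms at end of induction, no drug effect.** With 25% to 50% high in both arms, it rejects 1.0% to 1.3% of the time with 10 per arm and 0.8% to 2.1% with 8.

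**The case against.** The strongest reply is randomisation. Both arms receive the same induction and are judged against the same cut-off, so a shift unrelated to metformin is expected equally in each. The objective is already comparative, and Fisher's and chi-square tests are on the list. This stands as far as it goes: the cut-off does not bias a between-arm comparison. But the plan ties the change in expression only to McNemar's test, so the protection is available and not specified.

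Two stronger readings are tempting, and the documents do not support them.

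- *The cut-off makes a quarter to a half of healthy people 'high' by construction, and so produces the cited 50% shift by chance.* Only a median fixes the share above it. The shares in step 2 rest on assumed spreads, and the Problem statement says that expression in this population and its variation during treatment are unknown. The cut-off alone gives no net shift; that also needs a fall towards healthy levels. The cut-off behind the cited 50% cannot be checked here.
- *A higher threshold would cure the problem.* If late values are those of healthy people, a 95th-centile cut-off makes 95% of initially high patients low without a drug effect, and mean + 2 SD makes about 98%, against 50% at a log-scale mean. With about 20 patients, a survival group could also be nearly empty.

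It is also fair to say that the plan presents 'high' as a label relative to controls and never as a marker of resistance. The unstated scale and timing are mainly missing detail.

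**Conclusion.** The concern holds for the test of metformin. As written, the plan can report a high-to-low shift of 50% or more as a drug effect when none exists. If all patients start high and 50% to 75% become low, McNemar's test in one arm rejects 38% to 92% of the time with 10 patients and 15% to 68% with 8. A between-arm Fisher test rejects about 1% to 2%.

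This rests on the assumption that expression moves towards healthy levels as blasts clear, and on the assumed share of patients high at diagnosis; with 80% high the figures fall to 9% to 46%. The documents establish the unsorted assay, the two sampling times, the mean-based cut-off and the lack of a named between-arm test of change. They do not establish the size of any return to normal.

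**What to change.** 1. In Statistical analysis, make the test of metformin a between-arm comparison of end-of-induction expression or its change, for ABCB1/MDR1 and for AMPK. Continuous delta-Ct values adjusted for the diagnosis value are preferable; Fisher's exact test on the categories is the simpler alternative.
2. Keep McNemar's test within each arm as descriptive only, and say how the three categories are reduced to the two it needs.
3. If the high/low label is kept, compute the control mean on the delta-Ct scale, fix it once before arm and outcome are linked, and state the number of controls. Form the survival groups from the diagnosis sample.
4. Do not move to an upper-limit threshold.

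**Cost.** A few sentences and a little more analysis, with the same samples and assays. A within-arm shift could no longer be reported as a metformin effect. The between-arm test on categories is also weak at this size: with 10 per arm and 50% against 10% high at end of induction, Fisher's test has about 30% power. That is a further reason to prefer the continuous values.
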